3.3.2.1 Hematologic toxicities

Table 8. Dose Modification and Management of Hematologic Adverse Events

Observation	Action
On day 1 and 15 Absolute neutrophil count (ANC) \geq 1500/mcL AND Platelets \geq 75,000/mcL AND Hemoglobin \geq 8 g/dL	No interruption.
On day 1 and 15 ANC $<$ 1500/mcL OR Platelets $<$ 75,000/mcL OR Hemoglobin $<$ 8 g/dL	If any weekly evaluation demonstrates grade \geq 3 neutropenia or grade \geq 2 thrombocytopenia, a repeat hematology assessment will be obtained 2-4 days later. On first occurrence , hold the drug(s) causing the toxicity for up to 21 days until ANC \geq 1500/mcL, platelets \geq 75,000/mcL, and hemoglobin \geq 9 g/dL. The associate investigator and/or PI will determine whether one or both drugs are responsible for an observed toxicity and will initiate appropriate medical therapy and no change in dose upon re-initiation. On second occurrence , hold the drug(s) causing the toxicity for up to 21 days until ANC \geq 1500/mcL, platelets \geq 75,000/mcL, and hemoglobin \geq 9 g/dL. Initiate appropriate medical therapy. Treatment with olaparib or EP0057 may be restarted at one dose level (DL) lower. Patients whose counts have not recovered to ANC \geq 1500/mcL, platelets \geq 75,000/mcL, and hemoglobin \geq 9 g/dL after 21 days should be removed from the drug causing the toxicity.
At any time during cycle Grade 4 hematologic AE	On first occurrence , hold the drug(s) causing the toxicity for up to 21 days until ANC \geq 1500/mcL, platelets \geq 75,000/mcL, and hemoglobin \geq 9 g/dL. Initiate appropriate medical therapy. Treatment with olaparib or EP0057 may be restarted at one DL lower. On second occurrence , discontinue the drug(s) causing the toxicity. Follow patient until

Table 8. Dose Modification and Management of Hematologic Adverse Events

Observation	Action
	resolution/stabilization of toxicity. Patients whose counts have not recovered to ANC \geq 1500/mcL, platelets \geq 75,000/mcL, and hemoglobin \geq 9 g/dL after 21 days should be removed from the drug causing the toxicity. See section 3.3.2.1 for exceptions.
Toxicities requiring more than 2 dose reductions	Remove patient from the drug causing the toxicity.

- Treatment may be delayed for a maximum of 21 days after holding the treatment for toxicities that develop and do not resolve as defined above (the following AE's are exempt from hold: lymphopenia, or leukopenia in the absence of grade 3 or higher neutropenia).
- Weekly blood counts will be obtained during the first cycle, and then at day 1 and 15 of subsequent cycles.
- Management of prolonged hematological toxicities while on study treatment
 - If a patient develops prolonged hematological toxicity such as:
 - \geq 2 week interruption/delay in study treatment due to CTC grade 3 or worse anemia and/or development of blood transfusion dependence
 - \geq 3 week interruption/delay in study treatment due to CTC grade 3 or worse neutropenia (ANC $<$ 1,000/mcL)
 - \geq 3 week interruption/delay in study treatment due to CTC grade 3 or worse thrombocytopenia (Platelets $<$ 50,000/mcL)
 - Weekly differential blood counts including reticulocytes (calculate reticulocyte index (RI), RI = reticulocyte count x hematocrit (Hct)/normal Hct; a value of 45 is usually used for normal Hct) and peripheral blood smear should be performed. If any blood parameters remain clinically abnormal after 4 weeks of dose interruption, the patient should be referred to hematologist for further investigations. Bone marrow analysis and/or blood cytogenetic analysis should be considered at this stage according to standard hematological practice.
 - Development of a confirmed myelodysplastic syndrome or other clonal blood disorder should be reported as an SAE. Study treatment should be discontinued if diagnosis of myelodysplastic syndrome is confirmed.

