3.3.2 Dosing Delays/Dose Modifications and Management of Toxicities

- In the case of toxicity, appropriate medical treatment should be used (including anti-emetics, anti-diarrheals, etc.).
- Once a patient has a dose reduction for toxicity, the dose will not be increased.
- A maximum of 2 dose reductions is permitted
- If either agent is discontinued due to toxicity, the patient may continue on the other agent.
- Participants continuing to experience toxicity at the off treatment visit will be contacted for additional assessments until the toxicity has resolved or is deemed irreversible. Patients must remain on the study to have additional assessment.
- For AEs that are unrelated to the study drugs, study drug may be held for up to 21 days at the discretion of the PI.
- The associate investigator and/or PI will determine whether one or both drugs are responsible for an observed toxicity and will manage that toxicity as described below.

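### Table 8 gives two different first-restart doses for a grade 4 neutrophil or platelet count found on Day 1 or Day 15

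*Combined protocol and SAP*

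**What the plan says.** Two rows of Table 8 matter here.

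- **Second row (below threshold).** It applies on Days 1 and 15 when ANC is below 1500/mcL, platelets are below 75,000/mcL or hemoglobin is below 8 g/dL. At first occurrence the causative drug is held for up to 21 days until recovery; the investigator then "will initiate appropriate medical therapy and no change in dose upon re-initiation". At second occurrence: "Treatment with olaparib or EP0057 may be restarted at one dose level (DL) lower".
- **Third row (grade 4).** It applies to any "Grade 4 hematologic AE", at any point in the cycle. At first occurrence, after the same hold and recovery: "Treatment with olaparib or EP0057 may be restarted at one DL lower". At second occurrence the instruction is to "discontinue the drug(s) causing the toxicity".

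Section 3.3.2 adds two general rules: "Once a patient has a dose reduction for toxicity, the dose will not be increased" and "A maximum of 2 dose reductions is permitted".

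**The concern.** The second row does not exclude grade 4 counts, and the third row does not exclude Days 1 and 15. A patient whose grade 4 count is found on one of those days falls under both rows, and the rows give different restart doses. Whichever dose the investigator chooses departs from one row as written.

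The direction matters for safety. Read literally, the second row sends a patient back to full dose after a grade 4 count. Table 9 (section 3.3.3) restarts one level lower after a grade 3 non-hematologic event, so the second row would be more lenient for a worse grade. The toxicity classes differ, so this comparison does not prove an error, but it does suggest that the third row is the intended rule for grade 4.

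**Working it through.** The plan states no figure to reproduce. The check compares the two triggers and then works out the doses.

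**1. Does a grade 4 count always meet the second row?** The bullets after Table 8 define "CTC grade 3 or worse neutropenia" as ANC below 1,000/mcL, and the matching platelet limit as below 50,000/mcL. Grade 4 is worse than grade 3, so:
- grade 4 ANC < 1,000 < 1,500/mcL, the second-row limit;
- grade 4 platelets < 50,000 < 75,000/mcL, the second-row limit.

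The exact grade 4 cut-offs are not needed. The documents print no numeric grade 4 limit for hemoglobin, so the point is confined to neutrophils and platelets.

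**2. Do Days 1 and 15 fall in the third row?** Yes. It covers the whole cycle with no exception for those days. The bullets after Table 8 schedule blood counts weekly in cycle 1 and on Days 1 and 15 thereafter. From cycle 2 on, the overlap therefore falls on the routine count days named there.

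**3. Size at first restart, level 4R (Tables 6 and 7).**

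| Drug held responsible | Second row | Third row | Difference |
|---|---|---|---|
| Olaparib, twice daily | 250 mg | 200 mg | (250 − 200)/250 = 20% |
| EP0057, every 2 weeks | 12 mg/m² | 9 mg/m² | (12 − 9)/12 = 25% |

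Reductions used after the first event: 0 of 2 under the second row, 1 of 2 under the third. By section 3.3.2 the reduction cannot be reversed.

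**4. Second occurrence.** The conflict is softer. The second row permits a restart one level lower and the third row requires discontinuation, so discontinuing satisfies both.

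**5. Is there a tie-breaker?**
- The third row's pointer to exceptions leads back to section 3.3.2.1, where the bullets exempt from hold only lymphopenia, and leukopenia without grade 3 or higher neutropenia.
- Sections 3.6.1 and 14.1.6 give the 21-day limit on delay but no restart dose.
- Nothing else in sections 3.3.1 to 3.3.3 ranks the rows.

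**6. Does the event occur at this dose?** Section 1.2.16 reports one dose-limiting grade 4 neutropenia among six patients at level 4R: 1/6 = 16.7%, exact 95% CI 0.4% to 64.1%. This shows only that grade 4 neutropenia happens. The day of the count is not given, and shorter grade 4 episodes may not have counted as dose-limiting. Growth factors were barred in the phase I dose-limiting-toxicity period (section 3.3.2.2) but are recommended in phase II (section 3.2.2). The frequency of grade 4 counts on Day 1 or 15 in phase II cannot be derived from the documents, and none is assumed.

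**The case against.** The best reply is that the table settles the matter by its structure. The rows rise in severity, from adequate counts to below threshold to grade 4. On Days 1 and 15 the grade 4 counts are a subset of the below-threshold counts, so the third row is the narrower rule there. If the second row governed grade 4 counts on those days, the third row would have few routine counts to act on after cycle 1. This is good evidence of intent, and most clinicians would probably apply the third row. It is still inference. Taken as a whole, neither trigger contains the other, since one is specific on day and the other on grade, and no sentence gives precedence.

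A second reply is that *may* in the third row is permissive, so a full-dose restart is not expressly forbidden. The natural reading is that *may* governs whether to restart and that the stated level governs the dose. If it covered the dose as well, the third row would leave the restart dose unspecified.

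A third reply is that little follows in practice. The hold, the recovery counts and the 21-day limit are the same in both rows at first occurrence. This is a single-center trial whose team meets regularly to discuss each patient. Phase I is complete and the urothelial and prostate cohorts are closed to accrual, which leaves SCLC enrolment of up to 27 evaluable patients. All of that stands and keeps the point minor. It does not remove the contradiction.

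**Conclusion.** The conflict is real and minor. A drug-related grade 4 neutrophil or platelet count on Day 1 or 15 always meets both rows. At first occurrence, if the drug is restarted, no dose satisfies both: they differ by 20% for olaparib or 25% for EP0057 at the recommended phase 2 dose, and by one of the two permitted reductions.

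This rests on the current wording of Table 8, on the grade 3-or-worse limits printed after it, and on reading the third row's lower level as the dose at which treatment resumes. Grade 4 counts on other days fall under the third row alone. How many patients would be affected is unknown. No effect on the 16-week progression-free endpoint or on the design's error rates is claimed.

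**What to change.** At the next amendment, reword the heading of the second row so that it covers Day 1 and Day 15 counts below threshold that are not grade 4. Add one sentence stating that the third row governs every grade 4 hematologic event, including those found on Days 1 and 15. Leave the lymphopenia and leukopenia exemptions as they are.

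The cost is one row heading and one sentence, with no extra visits, tests or patients. The downside is that some patients will be reduced or stopped earlier than a literal reading of the second row would require.

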3.3.2.2 Neutropenia

- Phase I: Growth factors to prevent neutropenia will not be administered during the DLT period in phase I but may be used thereafter to prevent/treat neutropenia. Please note that G-CSF should not be used within at least 24 hours of the last dose of EP0057 administration.

3.3.2.3 Thrombocytopenia

- Thrombocytopenia will be treated conservatively. In the absence of bleeding, or a necessary invasive procedure, platelet transfusions should be given for a platelet count $\leq 10,000/\text{mCL}$.
- If invasive procedure(s) is (are) planned, or the patient develops bleeding, platelet transfusions should be administered in accordance with the standard of practice, usually maintaining a platelet count above 50,000/mCL.

3.3.2.4 Anemia

- Symptomatic anemia should be treated with red blood cell transfusion and is recommended if the hemoglobin falls below 8 g/dL or the patient is symptomatic.

3.3.3 General Recommendations for Dose Modification and Management of Non-Hematologic Adverse Events

- The management of general AEs not otherwise specified in the following sections should be as per **Table 9**.
- At the discretion of the investigator, the study drugs may be held or dose modified independently if the observed toxicity is attributed to only one of the drugs, while the patient continued to receive the drug not associated with the observed toxicity.
- Dose modifications for nausea, vomiting, and diarrhea will be made only if they are refractory to treatment. The time a given drug is held should not exceed 21 days.

Table 9. General Management of Adverse Events (Non-Hematologic)

Observation	Action
Grade 1 or 2 AEs resolves promptly (within 48 hours) with supportive care	Maintain dose level (DL)
Any \geq grade 3 non-hematologic*	Hold study drug(s) causing the toxicity for up to 21 days until toxicity resolves to \leq grade 1. Treatment with olaparib or EP0057 may be restarted at one DL lower, as per the dose reduction guidelines.
Grade 3 or 4 non-hematologic AE related to drugs that does not resolve to grade 1 or less within 21 days despite maximum supportive care after treating patient at the lowest reduced DL	Remove patient from the drug causing the toxicity.
Toxicities requiring more than 2 dose reductions	Remove patient from the drug causing the toxicity.

*Except fatigue/asthenia < 2 weeks in duration; mucositis in subjects who have not received optimal therapy for mucositis; vomiting or diarrhea lasting less than 72 hours whether treated with an optimal anti-emetic or anti-diarrheal regimen or not; or alkaline phosphatase changes

- Management of new or worsening pulmonary symptoms

If new or worsening pulmonary symptoms (e.g. dyspnea) or radiological abnormality occurs, an interruption in olaparib dosing is recommended and a diagnostic workup (including a high resolution CT scan) should be performed, to exclude active pneumonitis. Following investigation, if no evidence of abnormality is observed on CT imaging and symptoms resolve, then olaparib treatment can be restarted, if deemed appropriate by the investigator.

3.3.4 Management of the hypersensitivity/infusion reactions

Table 10. Management of the hypersensitivity/infusion reactions

Hypersensitivity reaction	
Grade 1 or 2	
Stop infusion immediately, continue hydration fluids and provide medications as indicated per institutional guidelines.
 
If symptoms resolve within 1-2 hours, at Investigator's discretion may re-start study drug administration at slower rate (i.e. 2x slower rate) and increase rate slowly to complete administration of full dose.
 
OR
 
Hold dose administration on day of event, and resume treatment at next scheduled day at same dose level.
 
At Investigator's discretion may administer subsequent dose using a desensitization protocol as per institutional guidelines.

Grade 3 or 4	
Stop infusion immediately and administer medical support as indicated per institutional guidelines.
 
Hold dose administration on day of event.
 
Review with study Principal Investigator to determine whether to discontinue from study drug treatment. Confirm that rate of administration was appropriate and premeds were given as suggested.

Administration of EP0057 should be over 2 hours (using the following infusion schedule) with additional pre-medications (dexamethasone 20mg IV, ranitidine 50mg IV, acetaminophen 650mg PO, ondansetron 16mg PO or IV and Benadryl 50mg PO).

EP0057 in 500ml 5% dextrose IV infusion

15mL/hr for 15 minutes, then increase to
30mL/hr for 15 minutes, then increase to
60mL/hr for 15 minutes, then increase to
120mL/hr for 15 minutes, then increase to

240mL/hr for 15 minutes, then increase to
480mL/hr for 15 minutes, then increase to
528mL/hr for 30 minutes to complete infusion

3.3.5 Dose Modification for Surgical Procedures or Palliative Radiation

- Olaparib should be stopped 3 days before surgery and re-started after wound has healed following recovery.
- No stoppage of olaparib is required for any biopsy procedures.
- Olaparib should be discontinued for a minimum of 3 days before a patient undergoes therapeutic palliative radiation treatment.

3.3.6 Laboratory safety assessment

Full hematology assessments for safety (hemoglobin, red blood cells [RBC], platelets, mean cell volume [MCV], mean cell hemoglobin concentration [MCHC], mean cell hemoglobin [MCH], white blood cells [WBC], absolute differential white cell count (neutrophils, lymphocytes, monocytes, eosinophils and basophils) and absolute neutrophil count or segmented neutrophil count and Band forms should be performed weekly during Cycle 1, at each subsequent visit, and when clinically indicated. If absolute differentials are not available, percentage differentials are acceptable. Coagulation [activated partial thromboplastin time (APTT) and international normalized ratio (INR)] will be performed at baseline and if clinically indicated. Patients taking warfarin may participate in this study; however, it is recommended that prothrombin time (INR and APTT) be monitored carefully at least once per week for the first month, then monthly if the INR is stable.

Biochemistry assessments for safety include an acute care panel and hepatic panel. These tests should be performed weekly during Cycle 1, at each subsequent visit, and when clinically indicated. The mCRPC cohort will have additional assessments specified in [3.4](#).

Urine or serum HCG for IOCBP (to be performed within 3 days of C1D1) is to be performed at screening only.

Bone marrow or blood cytogenetic samples may be collected for patients with prolonged hematological toxicities.

Additional analyses may be performed if clinically indicated.

Any clinically significant abnormal laboratory values should be repeated as clinically indicated.

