2.3.2 Screening activities performed after a consent for screening has been signed

The following activities will be performed only after the participant has signed the study consent OR the consent for study 01-C-0129 (provided the procedure is permitted on that study) on which screening activities may also be performed. Assessments performed at outside facilities or on another NIH protocol within the timeframes below may also be used to determine eligibility once a participant has signed the consent.

Screening must be completed within 2 weeks prior to C1D1.

- History and physical exam (including height, weight, vital signs and performance status)
- Blood tests (for organ function)
 - Complete blood count (CBC/Diff)
 - Acute care panel (sodium, potassium, chloride, total CO₂ (Bicarbonate), creatinine, glucose, urea nitrogen)
 - Hepatic panel (alkaline phosphatase, ALT/GPT, AST/GOT, total bilirubin, direct bilirubin)
 - Prothrombin time (PT)
 - Partial thromboplastin time (PTT)
 - Viral Markers Protocol Screen (HBsAg, anti-HCV, anti-HIV) within 3 months of C1D1.
- Collection of pathology reports from any certified laboratory for confirmation of diagnosis (may be done prior to the two week screening window).
- CT chest/abdomen/pelvis (mCRPC patients will have baseline CT scans and technetium-99 bone scan imaging within 30 days prior to initiation of therapy)
- Electrocardiogram
- Echocardiogram within 4 weeks prior to C1D1
- Urine or serum HCG for IOCBP (to be performed within 3 days prior to C1D1)
- Serum testosterone level (mCRPC patients only)

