2.5 BASELINE EVALUATION

Please refer to the Study Calendar (Section 3.4).

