3.4 STUDY CALENDAR

On study assessments can be performed within ± 7 days of the specified time, unless otherwise indicated. Treatments may be delayed up to 7 days to accommodate scheduling.

Procedure	Screening	Baseline ²	Cycles = 28 days ¹										End of Treatment/ Disease Progression ¹³	Post Therapy Follow-up ⁴
			Day 1	2	3	4	5	7	15 ²⁸	21	28	Cycle 2 ²² Day 1		
History	X											X	X	
Physical exam ³	X	X							X				X	
PTT/PT ²³	X	X												
Viral Markers Protocol Screen ¹⁷	X													
CBC diff ^{5, 20}	X	X						X ¹⁴	X	X		X	X	
Acute Care Panel ^{6,20}	X	X						X ¹⁴	X	X		X	X	
Hepatic Panel ^{7, 20}	X	X						X ¹⁴	X	X		X	X	
Mineral Panel (mCRPC only) ²⁴			X						X					
LDH, Creatine kinase, Uric Acid, Total Protein (mCRPC only)		X										X		
Pregnancy test ⁸	X	X										X		
CT scan ¹²	X ¹⁵	X											X	
CT c/a/p and bone scan (mCRPC only)	X	X										X ²⁵	X	
PSA (mCRPC only)		X										X ²⁵	X	
Clinical disease assessment		X										X	X	
ECG	X	X	X ²⁷						X ²⁷			X ²⁷		
Echocardiogram ²¹	X													
Whole blood, plasma, hair ²⁶ and saliva for correlative studies ^{9, 29}			Refer to tables in section 5. Table 11 – Phase 1 and Phase 2 SCLC; Table 13 – UC expansion; Table 14 – mCRPC expansion											

Procedure	Screening	Baseline ²	Cycles = 28 days ¹										End of Treatment/ Disease Progression ¹³	Post Therapy Follow-up ⁴
			Day 1	2	3	4	5	7	15 ²⁸	21	28	Cycle 2 ²² Day 1		
PK ^{16,29}			X	X	X				X ¹⁹					
Biopsies ¹⁰		X				X							X	
EP0057			X						X			X		
Olaparib ¹¹					X	X	X	X		X				
Follow-up phone call														X

¹ Number of cycles depends on disease progression and development of intolerable side effects

² Baseline procedures are performed within 2 weeks of initiation of study therapy with the exception of pregnancy test which must be performed within 3 days prior to the initiation of study therapy. If the procedure was performed during the appropriate timeframe at screening, it is not necessary to repeat at baseline.

³ Symptom-directed physical examinations will be performed as clinically indicated in the investigator's judgment

⁴ Follow-up for survival will be carried out every 3 months

⁵ Includes Neutrophils, Lymphs, Monos, Eos, Basos, WBC, RBC, Hemoglobin, Hematocrit, RBC Indices, MCV, RDW, Platelet. Results should be available prior to administration of study drugs

⁶ Includes Sodium (NA), Potassium (K), Chloride (CL), Total CO₂ (Bicarbonate), Creatinine, random Glucose, Urea or blood urea nitrogen [BUN], eGFR.

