⁷ Includes Alkaline Phosphatase, ALT/GPT, AST/GOT, Total Bilirubin, Direct Bilirubin

⁸ Only for IOCBP; may be obtained up to 3 days prior to Day 1 of each cycle.

⁹ Blood, plasma, hair and saliva samples will be collected at multiple time points during cycles 1,2 and each cycle thereafter for hair collection (for specific timepoints on correlative samples collection please refer to section 5.1.1 for Phase I and Phase II cohorts, section 5.1.2 for UC expansion cohort and section 5.1.3 for mCRPC expansion cohort). C1D15 timepoint for correlative studies will only be done for Phase II SCLC cohort. Only whole blood will be drawn for that cohort at that timepoint.

¹⁰ Optional biopsies will be obtained at baseline, during the first treatment cycle (approximately 24 hours after the first dose of olaparib) and at disease progression. In the mCRPC cohort, biopsy at baseline is mandatory.

¹¹ PO days 3-13 and days 17-26, as indicated in Section 3.2. There should be at least a 48-hour window between EP0057 and olaparib except dose level 5B which allows the interval to be abbreviated to 24 hours. Olaparib can be taken continuously if EP0057 is missed for any reason.

¹² Performed after every 2 cycles

¹³ Approximately 4 weeks after treatment discontinuation

¹⁴ Only done in cycle 1

¹⁵ Only done in phase 2

¹⁶ Phase 1 portion of the study in cycles 1 and 6 only.

¹⁷ Within 3 months of C1D1.

¹⁹ D15 PKs can be obtained +/- 5 days.

²⁰ Weekly during C1, at every visit for subsequent cycles, and whenever clinically indicated

²¹ Within 4 weeks

²² C2 and all subsequent cycles, Day 1

²³ All patients should get tested at screening. Patients taking warfarin will be monitored at least weekly for C1, then monthly if the INR is stable.

²⁴ Includes Albumin, Calcium, Magnesium and Phosphorus

²⁵ PSA is to be analyzed along with measurable lesions evaluated by CT scan of chest/abdomen/pelvis and technetium 99 bone scan every 3 cycles (every 12 weeks).

²⁶ Hair collection will only be done for Phase I cohorts.

²⁷ ECG required within 60 -180 minutes post-infusion for first two cycles of EP0057 for patients with any conduction abnormality on baseline ECG.

²⁸ Day 15 assessments not required for patients on olaparib only.

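### Section 3.3.6 restricts pregnancy testing to screening, while the study calendar schedules a test for every treatment cycle

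*Combined protocol and SAP*

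**What the plan says.** Section 3.3.6 (Laboratory safety assessment) gives the pregnancy-testing rule for individuals of childbearing potential (IOCBP) in one sentence: "Urine or serum HCG for IOCBP (to be performed within 3 days of C1D1) is to be performed at screening only".

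The Section 3.4 study calendar has its own row, "Pregnancy test", with marks under Screening, Baseline and Cycle 2 Day 1. Three footnotes govern how that row is read:

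- Footnote 22 defines the Cycle 2 column as "C2 and all subsequent cycles, Day 1".
- Footnote 8, attached to the pregnancy-test row, limits the test to IOCBP and says it "may be obtained up to 3 days prior to Day 1 of each cycle".
- Footnote 2 requires the baseline test within 3 days before therapy starts and adds: "If the procedure was performed during the appropriate timeframe at screening, it is not necessary to repeat at baseline".

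Section 2.3.2 lists the HCG test among the screening procedures, within 3 days before C1D1. It does not mention later cycles.

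**The concern.** The word *only* in 3.3.6 rules out later tests, so that section is not simply silent about them. The calendar schedules one for each cycle. A site cannot comply with both.

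Staff have reason to rely on 3.3.6. It is the protocol's laboratory safety section, and its hematology and biochemistry frequencies (weekly in Cycle 1, then at each visit and when clinically indicated) agree with calendar footnote 20. A reader who finds those in agreement has little cause to doubt the HCG sentence.

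What is at stake is participant safety. Section 4.2 rates the study drugs as carrying medium to high fetal risk, and Section 14.2.8 warns of fetal harm from olaparib. Section 3.6.1 makes pregnancy a reason for removal from therapy, and Section 8.6.1 requires treatment to stop at once. Those rules work only if a pregnancy is detected, and the per-cycle test is the only scheduled on-treatment check. Section 4 also notes that olaparib may weaken hormonal contraceptives, while Section 4.2.2 accepts hormonal methods combined with a condom.

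**Working it through.** The plan gives no count of pregnancy tests, so there is no figure to reproduce. The check sets the texts side by side and then counts tests.

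**1. The two schedules**

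| Time point | Section 3.3.6 | Section 3.4 calendar |
|---|---|---|
| Within 3 days before C1D1 | Test | Test (Screening and Baseline marks; footnote 2 lets one test serve for both) |
| Day 1 of Cycle 2 | None | Test (mark in that column; footnote 8 window) |
| Day 1 of Cycle 3 and later | None | Test at each (footnote 22) |

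The third mark in the calendar row lies ten columns after Baseline. That is the Cycle 2 Day 1 column, the same one that carries the Cycle 2 marks for history and CBC.

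**2. Does any text settle the conflict?**

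- Section 2.5 sends the reader to the calendar, but only for the baseline evaluation.
- Section 3.3.6 points to Section 3.4 only for the extra mCRPC assessments.
- Section 2.3.2 covers only the test before C1D1.
- No precedence clause was found, and nothing limits the Cycle 2 mark to one cohort or phase.

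**3. Number of scheduled tests at issue**

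Let N be the number of cycles a participant starts.

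- Section 3.3.6: 1 test.
- Calendar: 1 (before C1D1) + (N − 1) (Cycles 2 to N) = N tests. Screening and Baseline are not counted twice, because Section 2.3.2 places the screening test inside the baseline window.
- Possible omissions: N − 1.

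| N | Calendar | Section 3.3.6 | Possible omissions |
|---|---|---|---|
| 1 | 1 | 1 | 0 |
| 2 | 2 | 1 | 1 |
| 4 | 4 | 1 | 3 |

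N = 4 comes from the SCLC primary endpoint in Section 10.1 and the 28-day cycle: 16 weeks × 7 = 112 days, and 112 / 28 = 4 cycles, assuming treatment throughout without delay. The three tests at issue are those before Cycles 2, 3 and 4. N is not fixed; footnote 1 says: "Number of cycles depends on disease progression and development of intolerable side effects".

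**The case against.** The strongest reply accepts the conflict and disputes its weight and the choice of remedy.

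- **Likelihood.** Staff normally work from the study calendar, which has a dedicated row. Omitting every test is the worst case, and N − 1 says nothing about how probable it is. This stands: the documents show no missed test.
- **Population.** Phase I is complete, and accrual has ended in the mCRPC cohort (men only) and the urothelial cohort. New enrolment is confined to SCLC, capped at 27 evaluable patients, and only the IOCBP among them are affected. This also stands, although patients still on treatment in the urothelial cohort could be affected too.
- **Other safeguards.** The test before C1D1, contraception with a condom or abstinence, clinically indicated testing and pregnancy reporting within 24 hours all remain. They limit the consequence, but none is a routine on-treatment check. Clinically indicated testing generally depends on suspicion, and reporting depends on detection.
- **Intent.** The wording of 3.3.6 is explicit, and footnote 8 uses permissive language, so screening-only testing may have been intended. The documents do not settle this. However, footnote 8 sets the timing window; the calendar mark is what schedules the test. Even an optional per-cycle test would conflict with a screening-only rule.
- **No analytic effect.** Correct. That limits the severity but does not remove the conflict.

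**Conclusion.** The concern holds. Two current sections give incompatible pregnancy-testing schedules, and nothing in the protocol reconciles them. Following 3.3.6 as written removes all scheduled on-treatment tests: up to N − 1 for a participant who starts N cycles, or 3 for one treated without delay through 16 weeks. The count assumes one test per cycle under the calendar and a screening test that also serves as baseline.

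The conflict itself is certain. Whether tests would actually be missed is not known, and the number of IOCBP is not stated. No endpoint, decision rule or other statistical result is touched. This should be corrected as a participant-safety inconsistency; it does not threaten the trial's conclusions.

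**What to change.** Align Section 3.3.6 with the calendar, which is the safer and more detailed text. Suggested replacement for the HCG sentence:

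*For IOCBP, a urine or serum HCG test is required no more than 3 days before C1D1 and no more than 3 days before Day 1 of every later cycle.*

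This agrees with the calendar row, with footnotes 2, 8 and 22, and with the screening window in Section 2.3.2. If the sponsor did intend screening-only testing, it should say so, remove the Cycle 2 mark and amend footnote 8. Either way, one of the two texts has to change.

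The cost is a one-sentence amendment, which under the Statement of Compliance needs IRB review and approval before it takes effect; it could go into the next amendment. Relative to the calendar, no test is added. Relative to 3.3.6, it adds one inexpensive urine or serum test per cycle from Cycle 2, for IOCBP only, around a Day 1 visit that already includes CBC, acute care and hepatic panels.
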